9.7.2 Determination of Sample Size

A sample size of 12,000 subjects should provide the required power for the primary endpoints as follows: (revised per Amendment 02)

- For 460 MACE events to have occurred by approximately 43 months from start of the trial, providing 95% power to exclude a noninferiority margin of 1.4, assuming an annual background rate of 1.5%, 15-month accrual period, 5% annual drop-out rate, $\alpha = 0.025$, and a 1-sided test
- For 1401 MACE+ events to have occurred by approximately 54 months from the start of the trial, providing >85% power to detect a 15% risk reduction with lorcaserin HCl, assuming an annual background rate of 3.5%, 15-month accrual period, 5% annual drop-out rate, $\alpha = 0.05$, and a 2-sided test (revised per Amendment 02)

Key Secondary Endpoint (revised per Amendment 02)

- For 457 events of conversion to T2DM in subjects who are prediabetic at the time of enrollment (~33%) to have occurred by approximately 54 months from the start of the study, providing 86% power to detect a 25% risk reduction with lorcaserin HCl, assuming an annual background rate of 4%, 15-month accrual period, 5% annual dropout rate, $\alpha = 0.05$ and a 2-sided test. (revised per Amendment 02)

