## 5.2 STUDY SUBJECTS

#### **5.2.1** Definitions of Analysis Sets

The number (percent) of subjects included in each analysis set will be presented by analysis set, treatment group and overall. The description of the analysis data sets are:

- The Safety Analysis Set: will be the group of subjects who received at least one dose of study drug and had at least one post dose safety assessment.
- The Intent-to-Treat (ITT) Set: will be the group of all randomized subjects regardless of whether they took study drug or not. This is the same as the Full Analysis Set.
- Total Time Analysis Set: Using the ITT, events are counted that occur while subjects are on and off treatment. Subjects with no events will be censored at their last study contact or at the visit following Sponsor Notification of Study Completion, whichever

- occurs first. This analysis set will be used for the primary analysis. See Section 8.5 for censoring algorithm.
- On-Treatment plus 30 Days Analysis Set: Using the ITT, events are counted that occur
  while subjects are "on treatment" and up to 30 days from their last dose. Subjects with
  no events who discontinue early or complete the study will be censored at their last dose
  date plus 30 days. See Section 8 for definition of "on treatment" and Section 8.5 for
  censoring algorithm.
- On-Treatment Analysis Set: Using the ITT, events are counted that occur while subjects are "on treatment". Subjects with no events who discontinue early or complete the study will be censored at their last dose date. See Section 8 for definition of "on treatment" and Section 8.5 for censoring algorithm.
- Prediabetes Analysis Set: This set includes all subjects in the ITT set without a history of any type of diabetes and who are prediabetic at Baseline (defined in Section 8).
- Nondiabetes Analysis Set: This set includes all subjects in the ITT set without a history of any type of diabetes at Baseline (defined in Section 8).
- T2DM Analysis Set: This set will be all subjects in the ITT who have T2DM at Baseline (defined in Section 8).
- FDA-defined Valvulopathy Analysis Set: This set will be all subjects in the ITT without FDA- defined valvulopathy at Baseline (defined in Section 8.4). The data from the ECHO sub-study will be pooled with the ECHO data from the 3 pivotal lorcaserin HCl studies (APD356-009, APD356-010, and APD356-011).

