## 5.4.2 Key Secondary Analysis (revised per Amendment 02)

• Time to conversion to T2DM (Superiority). The estimate of the hazard ratio of lorcaserin HCl to placebo and the corresponding two-sided 95% CI will be calculated. The Prediabetes and Total Time Analyses Sets will be used as the primary analysis. The Prediabetes along with the On-Treatment Analysis Set and the On-Treatment plus 30 Days Analysis Set will be used as a sensitivity analysis at Study Completion (revised per Amendment 02).

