#### 8.5 CENSORING

The individual EOS date will be defined as the time of the last visit or study contact for each individual patient. If no event occurs for an endpoint, the earlier of the last study contact, the visit following Sponsor Notification of Study Completion or death will be treated as the censoring date.

MACE, MACE+ and conversion to T2DM events will be handled in the following manner according to their timing with respect to study milestones:

- Events that are recorded as beginning prior to the date of randomization will not be counted in the event analyses. The subject will be included in the analysis as not experienced the event. These events that are recorded as beginning prior to the date of randomization they will be included in a listing.
- Events that occur at any time after randomization and up to and including the first of the last visit/contact or visit following Sponsor Notification of Study Completion and reported *before* database lock will be adjudicated and included in all efficacy and safety analyses.
- Events that occur at any time after randomization and up to and including the last visit/contact and reported *after* database lock will be not be adjudicated and will not be included in the primary efficacy and safety analysis. They will be recorded in a tabular fashion as part of the final study report and may be included in sensitivity analyses.
- Events that occur after last visit/contact will not be included in the primary efficacy and safety analyses but may be included in the safety database if they fulfill safety reporting criteria.

Events in subjects who withdraw consent for clinical follow-up:

- All events that occur before withdraw of consent are included in analyses.
- Events that occur after withdraw of consent will be included in the primary analyses if they were found through vital status search prior to database lock.

Events in subjects who stop and re-start study medication.

• For the Total Time Analysis Set all events are counted regardless of whether the subject is on or off treatment.

- For the On-treatment Analysis Set events are counted only when the subject in "on-treatment". See Section 8, for definition of "on-treatment".
- For the On-treatment plus 30 days Analysis Set events are counted when the subject is "on-treatment" and up to 30 days from their last dose. See Section 8, for definition of "on-treatment".

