#### 8.5.2.2 Censoring for Conversion to T2DM

For subjects who experienced an event, their time-to-event will be determined from the randomization date to the date of first abnormal laboratory test as per the Diabetes CEC Diabetes Adjudication Charter, Appendix 13.1.4. The censoring variable will be, CENSORED=0. For subjects who do not experienced an event, the censoring time will be determined from the randomization date to the date described in the Table 6, using the Total Time on Study Analysis Set, along with a matching censoring variable, CENSORED=1. The above censoring algorithm

will be applied to both cohorts 1) subjects without any type diabetes at Baseline and 2) subjects with prediabetis at Baseline.

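### The SAP gives two censoring dates for the On-Treatment sensitivity analyses of T2DM conversion; pairing the Total Time date with on-drug-only events makes the hazard ratio depend on discontinuation

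*SAP*

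**What the plan says.** For the key secondary endpoint, SAP 5.4.2 uses the Prediabetes and Total Time sets as primary, and adds: "The Prediabetes along with the On-Treatment Analysis Set and the On-Treatment plus 30 Days Analysis Set will be used as a sensitivity analysis".

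The rules for those two sets are spread over four places in the SAP:

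- **5.2.1 (set definitions).** For the On-Treatment set: "Subjects with no events who discontinue early or complete the study will be censored at their last dose date". The plus 30 Days set adds 30 days. Both definitions refer to 8.5 for the algorithm.
- **8.5 (general censoring text).** This names conversion to T2DM among the events it governs. "For the On-treatment Analysis Set events are counted only when the subject in" the on-treatment state; the plus 30 Days set extends this to 30 days after last dose.
- **8.5.2.1 (MACE, MACE+, components, all-cause mortality).** The censoring date differs by analysis set. Table 6 has a Total Time row and two last-dose rows, and the on-treatment clocks start at first dose.
- **8.5.2.2 (conversion to T2DM).** Event subjects run from randomization to first abnormal laboratory test. Event-free subjects run from randomization "to the date described in the Table 6, using the Total Time on Study Analysis Set". There is no on-treatment branch.

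Off-drug follow-up exists for this endpoint. SAP 3.3 keeps subjects in the study after they stop drug, and a footnote to Protocol Table 4 requires glycemic measurements regardless of study drug status.

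**The concern.** A programmer building the on-treatment T2DM datasets finds one censoring date in the set definition and another in the endpoint's own rule. Because 5.2.1 defers to 8.5, the second date appears to govern.

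Read literally, Section 8.5 then supplies an event rule (on-drug conversions only) and a censoring date (final disposition) that do not belong together. A subject who stops drug and converts later is not an event, yet stays in the risk set to the end of follow-up. That off-drug time can add only to the denominator, so each arm's rate is diluted according to its off-drug share. If the shares differ, the hazard ratio moves for a reason unrelated to drug effect.

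At stake is the usefulness of the two analyses meant to show whether the T2DM result holds on drug. An unresolved choice of date also leaves room to choose after results are seen.

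**Working it through.** **1. The plan's own figure.** Protocol 9.7.2 expects 457 conversions by month 54. It gives the power and assumptions as "providing 86% power to detect a 25% risk reduction with lorcaserin HCl, assuming an annual background rate of 4%, 15-month accrual period, 5% annual dropout". Alpha is 0.05, two-sided.

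- Prediabetic subjects: 0.33 × 12,000 = 3,960, or 1,980 per arm.
- Events per arm = 1,980 × λ/s × [1 − (e^(−3.25s) − e^(−4.5s))/(1.25s)], with s = λ + 0.05. The inputs are 54 months = 4.5 years and 15 months' accrual = 1.25 years.
- Placebo (λ = 0.04): 258.8. Lorcaserin (λ = 0.03): 197.7. Total 456.5, against 457 stated.
- Power (Schoenfeld): √457/2 × |ln 0.75| − 1.96 = 3.075 − 1.960 = 1.115, giving 86.8%. The Freedman form gives 86.3%. Stated: 86%.

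The sample size reproduces and is not in question.

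**2. Three ways to read the censoring text**

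| Reading | Events counted | Event-free subjects censored at | Result |
|---|---|---|---|
| 5.2.1 whole | on drug (or +30 days) | last dose (or +30 days) | a proper on-treatment analysis |
| 8.5.2.2 whole | all conversions | Total Time row | repeats the primary analysis |
| 8.5 event rule with 8.5.2.2 date | on drug (or +30 days) | Total Time row | off-drug time with no possible event |

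**3. Size of the shift under the third reading.** Plan inputs are λ = 0.04 (placebo) and 0.03 (lorcaserin), drop-out hazard q = −ln 0.95 = 0.0513, and mean follow-up T = 4.5 − 1.25/2 = 3.875 years. The drug-discontinuation hazard d in each arm is an assumption. With s = λ + d + q:

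- On-drug person-years per subject: P = (1 − e^(−sT))/s
- On-drug events per subject: E = λP
- Retained off-drug person-years: R = d/(λ + d) × [(1 − e^(−qT))/q − P], where (1 − e^(−qT))/q = 3.514

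Placebo, d = 0.12: P = 2.646, E = 0.1058, R = 0.75 × 0.869 = 0.651. The rate is 0.1058/3.297 = 0.03210.

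Lorcaserin, d = 0.14: P = 2.602, E = 0.0781, R = 0.8235 × 0.912 = 0.751. The rate is 0.0781/3.353 = 0.02328.

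The ratio is 0.02328/0.03210 = 0.725. Censoring at last dose gives (0.0781/2.602)/(0.1058/2.646) = 0.75.

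| Discontinuation per year, lorcaserin / placebo (assumed) | True 0.75 becomes | True 1.00 becomes |
|---|---|---|
| 12% / 12% | 0.751 | 1.000 |
| 14% / 12% | 0.725 | 0.966 |
| 16% / 12% | 0.701 | 0.933 |
| 12% / 14% | 0.777 | 1.035 |

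At 12% in both arms about 20% of retained person-time is off drug (0.651/3.297 = 0.198 in placebo), yet the ratio hardly moves.

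**4. Check with the Cox model.** These are large-sample solutions of the partial-likelihood score equation with the same event rate, accrual and drop-out:

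| Lorcaserin / placebo (assumed) | True 0.75 becomes | True 1.00 becomes |
|---|---|---|
| 10% / 10% | 0.752 | 1.000 |
| 12% / 10% | 0.726 | 0.965 |
| 15% / 10% | 0.689 | 0.917 |
| 10% / 12% | 0.779 | 1.036 |
| 10% / 15% | 0.820 | 1.091 |

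Last-dose censoring returns 0.750 or 1.000 throughout. The plus 30 Days set behaves almost the same: 0.692 at 15%/10% and 0.817 at 10%/15%.

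A simulation of 60,000 subjects per scenario, with a true value of 0.75, agrees. At 15%/10% it gave 0.738 with last-dose censoring and 0.680 with the Total Time date. At 10%/15% it gave 0.779 and 0.846. The standard error of the log hazard ratio was about 0.027.

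**The case against.** The best defence is that 8.5.2.2 was written for the Total Time analysis only. SAP 8.5.2.4 uses almost the same phrase for an analysis it has just declared to be Total Time. Section 8.5.2.2 also says its algorithm serves both the non-diabetes and prediabetes cohorts, and on-treatment analyses are listed only for prediabetes. On this view the on-treatment date comes from 5.2.1 and the last-dose rows of Table 6. The reading is plausible, but 8.5.2.2 does not state that limit. Section 5.2.1 sends the reader to 8.5 for the algorithm, and the last-dose rows sit in a subsection whose title does not include T2DM.

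A reader might infer that 8.5.2.2 itself discards off-drug conversions. It does not: its event wording has no on-drug limit, and applied whole it simply repeats the primary analysis. The exclusion comes from 5.2.1 and 8.5, and the distortion needs that event rule together with the 8.5.2.2 date. No sentence spells out the pairing; it follows from reading 8.5 and its subsection together.

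The censoring diagrams in the SAP appendix are not reproduced in the public text, so whether they cover T2DM cannot be told. Section 8.5.2.2 does not cite them.

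The objection that the size rests on assumed discontinuation rates stands in full. The exact return to 0.75 under last-dose censoring also follows from assuming constant hazards and discontinuation unrelated to conversion risk. It is not evidence that an on-treatment analysis is unbiased in practice.

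**Conclusion.** The conflict is real and should be resolved: two censoring dates for the same two analyses, one of which gives a wrong result when paired with the on-treatment event rule in 8.5. Under assumed constant rates, a 2-point annual gap in discontinuation moves a true 0.75 to about 0.73 or 0.78. A 5-point gap moves it to about 0.69 or 0.82. Equal rates move it by about 0.002 at most.

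Two further inferences are not supported. One is that the error favours lorcaserin: the direction depends on which arm stops drug more, and the documents do not say. The other is that the key secondary result is compromised: its primary analysis uses the Total Time set, where the 8.5.2.2 date is correct. Alpha, the gatekeeping sequence and the sample size are unaffected. The consequence is confined to two sensitivity analyses.

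**What to change.** In SAP 8.5.2.2, limit the present text to the Total Time analysis and add, for the prediabetes on-treatment analyses:

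- **Events:** only conversions on treatment count (On-Treatment set), or on treatment and up to 30 days after last dose (plus 30 Days set).
- **Censoring:** event-free subjects take the matching last-dose row of Table 6.
- **Time origin:** first dose, as 8.5.2.1 does for MACE and MACE+. Section 8.5.2.2 now uses randomization. The protocol has the first dose taken at the randomization visit, so this should change few times, but it should be stated.

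Changing the censoring date alone would leave the unrestricted event wording and the different clock in place. The cost is a few sentences and one re-derived time-to-event dataset for two sensitivity analyses, with no change to data collection or testing. It should be settled before unblinding.

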#### 8.5.2.3 Censoring for Secondary Time-to-Event Endpoints

The censoring algorithm is the same for all secondary time-to-event endpoints and across the different Analysis Sets. Since all the Analyses Sets used the ITT population for these secondary endpoints, then for subjects who experienced an event, their time-to-event will be determined from the randomization date to the date of the event. The censoring variable will be, CENSORED=0. For subjects who do not experienced an event, the censoring time will be determined from the randomization date to the date described in Table7, along with a matching censoring variable, CENSORED=1.

Table 7 Censoring Date for Subjects who did not Experience an Event at Study Completion for Secondary Renal and Clucose Homeostasis Endnoints

Secondary Renal and G	lucose Homeo	stasis Endpoints	
	Analysis		Withdrawal From Study Follow-
Time-to-Event Endpoint	Set a	Completed the Study	up
New onset of renal	T2DM	In the Final Study	In the Final Study Disposition
impairment or		Disposition Form use the	Form use the date from, Date of
worsening of existing		date from;	Final Sponsor
renal impairment in		Date of Final Sponsor	Notification/Premature Study
subjects with T2DM at		Notification/Premature	Discontinuation
Baseline		Study Discontinuation	and
New onset of renal	Total Time	and status is equal to	status for discontinuation equals
impairment or		completed	any of the following;
worsening of existing			Withdrew Consent
renal impairment in all			Lost to Follow up
subjects enrolled in the			Study Terminated by Sponsor
study			• Death
Improvement in renal	T2DM		• Other
function	12DNI		
Tunction			
New onset of renal	Prediabetes		
impairment or	riediabetes		
worsening of existing			
renal impairment in			
subjects with			
prediabetes at Baseline			
Conversion to normal	Prediabetes		
glucose homeostasis	1 iculaucies		
a See Section 5.2.1 for det	finitions of An	alvsis Sets	1
500 50000011 5.2.1 101 del	11111110110 01 7 1111	11 J D 10 D D 0 0	

#### 8.5.2.4 Censoring for Sensitivity Analysis Time-to-Event Endpoints

Subjects that start another weight reduction medication or has a bariatric procedure: MACE and MACE+ endpoints will be analyzed using the Total Time Analysis Set.

For subjects who experienced an event and did not start on another weight reduction medication or did not have bariatric surgery, their time-to-event will be determined from the randomization date to the date of the event. The censoring variable will be, CENSORED=0.

For subjects who experienced an event and started on another weight reduction medication or undergoes bariatric surgery, the censoring variable will be, CENSORED=0, if date of event is either prior to date of starting a weight reduction medication or having bariatric surgery or the event occurred after having stopped taking a weight reduction medication. Their time-to-event time will be determined from randomization date to date of the event. The censoring variable will be, CENSORED=1, if the date of event is equal to or greater than date of having bariatric surgery or the event date occurred while on a weight reduction medication. The censoring time will be determined from the randomization date to the earliest date of starting another weight reduction medication and/or having bariatric surgery. If date of starting another weight reduction medication or having bariatric surgery is prior to the randomization date, then censoring time will be set to the randomization date.

For subjects who do not experience an event and did not start on another weight reduction medication or did not have bariatric surgery, the censoring time will be determined from the randomization date to the date described in the Table 6 using the Total Time on Study Analysis Set, along with a matching censoring variable, CENSORED=1.

For subjects who do not experience an event and start on another weight reduction medication or undergoes bariatric surgery, the censoring time will be determined from the randomization date to the date of starting a weight reduction medication or the date of the bariatric surgery, along with a matching censoring variable, CENSORED=1. If date of starting another weight reduction medication or having bariatric surgery is prior to the randomization date, then censoring time will be set to the randomization date.

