- Time to MACE:** The estimate of the hazard ratio of lorcaserin HCl to placebo and the corresponding 1-sided 97.5% confidence interval (CI) will be calculated. Noninferiority of lorcaserin HCl to placebo will be declared if the upper limit of the 97.5% CI is less than the noninferiority margin of 1.4. The Total Time Analysis Set will be used as the primary analysis at the interim analysis. (revised per Amendment 02) The On-Treatment Analysis Set and the On-Treatment plus 30 Days Analysis Set will be used as sensitivity analyses at study completion. (revised per Amendment 02)
- Time to MACE+:** The estimate of the hazard ratio of lorcaserin HCl to placebo and the corresponding 2-sided 95% CI will be calculated. The Total Time Analysis Set will be used as the primary analysis. (revised per Amendment 02) The On-Treatment Analysis Set and the On-Treatment plus 30 Days Analysis Set will be used as sensitivity analyses.

The incidence rate difference and the incidence rate ratio between lorcaserin and placebo will also be analyzed as supportive analysis for the primary endpoints above at study completion. (revised per Amendment 02)

Sensitivity analysis will be performed at study completion for the MACE and MACE+ endpoints using the Total Time Analysis Set. (revised per Amendment 02) This sensitivity analysis will not count a MACE or MACE+ event that occurs after the subject starts another weight reduction medication or undergoes bariatric surgery. (revised per Amendment 02)

KEY SECONDARY ENDPOINT ANALYSIS (revised per Amendment 02)

- **Time to conversion to T2DM:** The estimate of the hazard ratio of lorcaserin HCl to placebo and the corresponding 2-sided 95% CI will be calculated. The Prediabetes and Total Time Analyses Sets will be used as the primary for this analysis. The Prediabetes along with the On-Treatment Analysis Set and the On-Treatment plus 30 Days Analysis Set will be used as a sensitivity analysis at study completion (revised per Amendment 02).

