Change wording on censoring algorithm in subjects who started a weight reduction drug or had bariatric surgery.	In order to capture subjects who started a weight reduction drug or had bariatric surgery prior to randomization their censoring time is set to randomization date. In addition, for subjects who experienced an event after stopping a weight reduction drug the event will be counted.	• Section 8.5.2.4	
Exploratory Endpoint: Obesity Staging analysis will not be performed  • Proportions of subjects with at least a 1-stage reduction in an obesity-related complication (prediabetes, metabolic syndrome, T2DM, hypertension, and hypertriglyceridemia/dyslipidemia), incidence of other obesity-related complications will be collected	This population will show no change since Obesity Stage will be 1 for all subjects. In addition the study is not collecting all of the Obesity Staging variables to make a reliable interpretation.	• Section 7	

Previous Version: V2.0 Current Version: V3.0

Date of Revisions: 18 May 2018

Change	Rationale	Affected Section(s)
through AE reports, medical history, and use of concomitant medications, will be analyzed using logistic regression including treatment as factor. Comparison between lorcaserin HCl and placebo will be made at 1 year and EOS. The odds ratio, p-value and 2-sided 95% CI will be calculated. The ITT Analysis Set will be used for this analysis.		
Exploratory Endpoint: Obesity Staging analysis will not be performed  Proportion of subjects with reduction in the number of OAD medications or reduction in the dosage of OAD medications in the following subpopulations of subjects with T2DM at Baseline	It would be difficult to interpret results and data was not collected in order to answer this question	• Section 7
Included sentence "In addition, systolic and diastolic blood pressure will be summarized by clinically notable changes (see Section 8):	As per clinical	• Section 5.6.4
Definition of clinically notable changes for systolic and diastolic blood pressure was added.	As per clinical	• Section 8

Previous Version: V1.0 Current Version: V2.0

Date of Revisions: 31 March 2017

Change	Rationale	Affected Section(s)
As per protocol Amendment 02	Protocol was Amendment to remove conversion to T2DM as a co-primary endpoint and secondary endpoints were re- grouped	
 
Section 3.1, 3.2
 
Section 4
 
Section 5.1
 
Section 5.3.3
 
Section 5.4.1
 
Section 5.4.2
 

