## 5.4.1.1 Additional Sensitivity Analyses at Study Completion

- **Time to MACE (Non-inferiority):** The primary safety analysis above, which will be conducted at the interim analysis, will be repeated at study completion as a sensitivity analysis.
- Time to MACE (Superiority): The estimate of the hazard ratio of lorcaserin HCl to placebo and the corresponding one-sided 97.5% confidence interval (CI) will be calculated. Superiority lorcaserin HCl to placebo will be declared if the upper limit of the 97.5% CI is less than 1. The Total Time Analysis Set, the On-Treatment Analysis Set, and the On-Treatment plus 30 Days Analysis Sets will be used.
- The incidence rate difference and the incidence rate ratio between lorcaserin and placebo will also be analyzed as supportive analysis for each of the primary endpoints above. The adjusted risk difference (incidence rate difference) and relative risk (incidence rate ratio) along with their respective 95% CI will be estimated using a Poisson regression model (using PROC GENMOD in SAS) with a robust error variance (sandwich error estimator). The model will include factors for treatment and stratification variable (presence of established CV disease or CV risk factors without established CV disease). The Total Time Analysis Set, the On-Treatment Analysis Set, and the On-Treatment plus 30 Days Analysis Sets will be used.
- Subjects that start another weight reduction medication or had bariatric procedure: For MACE and MACE+ endpoints using the Total Time Analysis Set. In this sensitivity analysis subjects will be censored when the subject starts another weight reduction medication or undergoes a bariatric procedure.
- Subjects who permanently down titrate from BID dosing to QD dosing: For MACE and MACE+ endpoints using the On-treatment and On-treatment plus 30 days Analyses Sets. In this sensitivity analysis events will be not counted when the subject is on QD dosing.
- **Subjects who prematurely discontinued:** For the MACE (Superiority) and MACE+ endpoints, multiple imputation will be used to impute censored data for those subjects who are lost to follow-up. The Total Time Analysis Set will be used.

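### SAP 8.5.2.4 keeps follow-up after another weight-loss drug only when it ends in an event after stopping, contrary to SAP 5.4.1.1 and protocol 9.7.1.6

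*SAP*

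**What the plan says.** Protocol 9.7.1.6 states that this sensitivity analysis "will not count a MACE or MACE+ event that occurs after the subject starts another weight reduction medication" or undergoes bariatric surgery. SAP 5.4.1.1 turns that into censoring: "subjects will be censored when the subject starts another weight reduction medication or undergoes a bariatric procedure". Neither makes an exception for a drug that was later stopped.

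SAP 8.5.2.4, which holds the programming rule, differs by outcome:

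- **Subject with an event.** The event counts (CENSORED=0) if it came before the start of the drug or surgery, "or the event occurred after having stopped taking a weight reduction medication". For counted events, "Their time-to-event time will be determined from randomization date to date of the event". An event while on the drug is censored at the start. An event is also censored "if the date of event is equal to or greater than date of having bariatric surgery".
- **Subject without an event.** Censoring runs from randomization "to the date of starting a weight reduction medication or the date of the bariatric surgery", with no provision for a drug that was stopped.
- **Start before randomization.** In both cases, "then censoring time will be set to the randomization date".

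The SAP V3.0 change log shows that the exception was deliberate: "for subjects who experienced an event after stopping a weight reduction drug the event will be counted". It gives no matching rule for event-free subjects. SAP Section 7 (Changes in the Planned Analyses) lists two dropped exploratory endpoints and not this departure from the protocol.

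**The concern.** A censoring rule should not depend on what happens after the censoring date. Here it does. Of two subjects with identical start and stop dates, the one with a later event keeps the event and all follow-up, while the event-free one loses everything after the start. Each starter who stops can then add events with almost no matching event-free time, which inflates the event rate in whichever arm has more starters.

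The analysis exists to show whether the MACE and MACE+ results hold up when other weight-loss therapy is set aside. That question matters most when use differs by arm, and that is when this rule creates a difference by itself. In addition, SAP 5.4.1.1 and 8.5.2.4 cannot both be programmed.

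**Working it through.** **1. The rules side by side.** Let a subject start another weight-loss drug at time s after randomization and stop it at p. The event is at e, or follow-up ends event-free at c.

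| Course | SAP 5.4.1.1 | SAP 8.5.2.4 |
|---|---|---|
| Event before the start (e < s) | event at e | event at e |
| Event on the drug (s ≤ e ≤ p) | censored at s | censored at s |
| Event after stopping (e > p) | censored at s | event at e, full time kept |
| Stopped, no event | censored at s | censored at s |
| Surgery only, event afterwards | censored at surgery | censored at surgery |
| Surgery only, no event | censored at surgery | censored at surgery |

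Only the third row differs, and the fourth row has no matching change. Surgery alone is handled the same way with or without an event. A subject who stopped a drug, later had surgery and then had an event meets both the CENSORED=0 and the CENSORED=1 condition of 8.5.2.4; no precedence is given.

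**2. Design figures (protocol 9.7.2), reproduced as a baseline.** Power = Φ(√d/2 × |ln HR| − 1.96).
- MACE+: d = 1401, HR 0.85: Φ(18.72 × 0.1625 − 1.96) = Φ(1.08) = 86.0%, which agrees with >85%.
- MACE: d = 460, margin 1.4: Φ(10.72 × 0.3365 − 1.96) = Φ(1.65) = 95.0%, as stated.

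**3. Effect of the rule.** From the protocol: MACE+ 3.5% per year, 15-month accrual, 54-month cut, 5% annual dropout. Assumed: shares of starters, start uniform over years 0 to 3, six months of use, starting unrelated to risk. Cox hazard ratios come from 3 million simulated subjects per arm with a true ratio of 1.

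| Starts, placebo/lorcaserin | 8.5.2.4, all stop | 8.5.2.4, half never stop |
|---|---|---|
| 5%/5% | 1.000 | not run |
| 2%/1% | 0.996 | 0.998 |
| 4%/2% | 0.991 | 0.996 |
| 2%/4% | 1.009 | 1.005 |
| 10%/5% | 0.977 | 0.989 |
| 5%/10% | 1.023 | 1.012 |

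Censoring everyone at the start gives 0.9997 to 1.0003; removing only time on the drug gives 0.9999. For MACE at 1.5% per year, 8.5.2.4 gives 0.991 (4%/2%) and 0.976 (10%/5%). With equal use and a true ratio of 0.85, all three rules give 0.849 to 0.850.

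**4. Hand check at 4%/2%.** Scaled to 6,000 per arm, 12.3 placebo and 6.1 lorcaserin post-stop events are counted among 1,378, or about 689 per arm. The excess is (12.3 − 6.1)/689 = 0.9%, so the ratio is about 0.991.

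**5. Why it happens.** Per 100 starters the rule keeps 5.8 post-start events but only 9.6 of 217 post-start person-years. The apparent post-start rate is 5.8/9.6 = 0.60 per person-year, against a true 0.035.

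**6. Larger use.** With constant yearly start rates instead, and use of three to six months, 4%/2% per year gives about 0.97 to 0.98. At 5%/1% per year (about 903 and 195 starters per 6,000) the ratio is about 0.94 to 0.95.

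**7. Use that ended before randomization.** Per 100 such users the rule keeps all 11.5 events but 21 of 329 person-years. With 10% in each arm the ratio is still 1.000.

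**The case against.** **Size.** This is one sensitivity analysis outside the gatekeeping of SAP 5.3.3. With 1,378 events the standard error of the log hazard ratio is 2/√1378 = 0.054, so 0.991 is a shift of 0.009/0.054 = 0.17 standard errors. Protocol 9.4.7.2 prohibits other weight-loss products and exclusion 15 bars planned bariatric surgery, so use may be low. All this stands and limits the severity; it does not reconcile the contradictory texts.

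**Censoring at the start is not clearly better.** If would-be starters carry 1.5 times the risk in both arms, ratios at 4%/2% and 10%/5% are 0.993 and 0.982 under 8.5.2.4, against 1.005 and 1.014 when censoring at the start. If, in addition, half never stop, 8.5.2.4 comes closer to 1 (0.999 and 0.997) than censoring at the start (1.0055 and 1.014). This stands as a caution, but 8.5.2.4 does well there only because two errors offset. Removing only time on the drug gives 1.001 and 1.003 in the first of these settings.

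**Start before randomization.** The sentence setting the time to the randomization date could apply to all such subjects, whatever their outcome. That reading is possible but less natural, since the sentence fixes only the censoring time. Few such users may be on record: exclusion 7 bars use within a month of Screening, and protocol 9.4.7 collects most other medication for only 30 days before first dose.

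**Disclosure.** The change is logged in V3.0, and protocol 9.7.5 sends SAP revisions to the study report. So nothing is hidden, but SAP 5.4.1.1 was left unchanged.

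**Conclusion.** The concern holds. SAP 8.5.2.4 conflicts with SAP 5.4.1.1 and protocol 9.7.1.6, and it keeps post-start follow-up only when that follow-up ends in an event after stopping. The distortion is nil at a true ratio of 1 with equal use, about 1% or less at starts up to 4%/2%, and about 2% at 10%/5% if all stop. Its direction is unknown because the documents give no use by arm. These sizes rest on the assumed shares, six months of use and, except where stated, starting that is unrelated to risk. The primary Cox analyses, event targets and gatekeeping do not change. The point should be corrected, but it does not threaten the main conclusions.

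**What to change.** Adopt one rule that does not look at the outcome, and use it in every place.

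- **Option A**, in line with SAP 5.4.1.1 and the protocol: censor every subject at the first post-randomization start of another weight-loss drug or bariatric procedure, and delete the after-stopping clause. State the assumption that starting is unrelated to event risk.
- **Option B**, if post-stop events are wanted: remove only the interval on the drug and keep post-stop time for everyone who stopped, with or without an event. Amend SAP 5.4.1.1 and list the departure from protocol 9.7.1.6 in SAP Section 7. B can also be reported beside A as a check on informative censoring.

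Under either option, treat use before randomization alike for subjects with and without events (for example, ignore use that ended before randomization). If B is chosen, also state which condition prevails when a stopped drug is followed by surgery.

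The cost is SAP wording and minor reprogramming, with no new data. A loses a few post-stop events and may itself censor informatively; B needs usable start and stop dates.

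Two separate clarifications to SAP 5.4.1.1 could be made at the same time. State that time on QD dosing leaves the risk set along with the events not counted there. Either specify a log person-time offset for the Poisson model or label its results as risk ratio and risk difference.
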